2.2 Analysis sets

Treatment group will be named as: Non Surg BGJ398 125 mg and Surg BGJ398 125 mg. If there are no patients in the surgery group, only Non Surg BGJ398 125 mg will be presented.

Full Analysis Set

The Full Analysis Set (FAS) includes all patients who received at least one dose of BGJ398. The FAS will be used for all listings of raw data. Unless otherwise specified the FAS will be the default analysis set used for all analyses.

Per protocol set (PPS)

The Per-Protocol Set (PPS) will consist of a subset of patients in the FAS (with FGFR1-TACC1, FGFR3-TACC3 and/or activating mutations in FGFR1, 2 or 3) who are compliant with requirements of the CSP. The PPS will include patients who have an adequate tumor assessment at baseline, a follow-up tumor assessment >8 weeks after starting treatment unless disease progression is observed before that time, and no protocol deviations.

[figure not shown]
Safety

The Safety Set includes all patients who received at least one dose of BGJ398 and have at least one valid post-baseline safety assessment.

The statement that a patient had no AE (on the AE (e)CRF) constitutes a valid safety assessment.

The treatment received is defined as:

- The treatment assigned if it was received at least once, or
- The first treatment received when starting therapy with study treatment if the assigned treatment was never received.

Patient Classification:

Patients may be excluded from the analysis populations defined above based on the protocol deviations entered in the database and/or on specific subject classification rules defined in Table 2-3.

Table 2-3 Determination of analysis set membership

Description used to report Protocol Deviations	Protocol deviation IDs	Analysis set(s) to be excluded
Inclusion criteria not met	INC01, INC02, INC04	PPS
Use of prohibited concomitant medication	WITH04, WITH05, TRT05	PPS

Withdrawal of Informed Consent

Any data collected in the clinical database after a subject withdraws informed consent from all further participation in the trial, will not be included in the analysis. The date on which a patient withdraws full consent is recorded in the (e)CRF.

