10.1.3 Per-Protocol Set

The Per-Protocol Set (PPS) will consist of a subset of patients in the FAS (with FGFR1-TACC1, FGFR3-TACC3 and/or activating mutations in FGFR1, 2 or 3) who are compliant with requirements of the Clinical Study Protocol (CSP). The PPS will include patients who have an adequate tumor assessment at baseline, a follow-up tumor assessment >8 weeks after starting treatment unless disease progression is observed before that time, and no major protocol deviations.

All major protocol deviations leading to exclusion from the PPS will be detailed in the Reporting and Analysis Plan (RAP).

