14.3.1.2 Evaluable for objective response

Only those participants who have measurable disease present at baseline (Cycle 1, Day 1 scan) or post-operatively (group 2) and have received at least one dose of therapy will be considered evaluable for response. These participants will have their response classified according to the definitions stated below. (Note: Participants who exhibit objective disease progression or die prior to the end of Cycle 1 will also be considered evaluable.)

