- d. Clear clinical deterioration not attributable to other causes apart from the tumor (e.g., seizures, medication side effects, complications of therapy, cerebrovascular events, infection, etc.). The definition of clinical deterioration is left to the discretion of the investigator but it is recommended that a decline in the KPS from 100 or 90 to 70 or less, a decline in KPS of at least 20 from 80 or less, or a decline in KPS from any baseline to 50 or less, for at least 7 days, be considered neurologic deterioration unless attributable to comorbid events or changes in corticosteroid dose. Similarly, a decline in the Eastern cooperative Oncology Group (ECOG) performance scores from 0 or 1 to 2 or 2 to 3 would be considered neurologic deterioration, unless attributable to co-morbid events or changes in corticosteroid dose.
- e. Failure to return for evaluation due to death or deteriorating condition
- f. Patients with non measurable enhancing disease whose lesions have significantly increased in size and become measurable (minimal bidirectional diameter of ≥ 10 mm and visible on at least two axial slices that are preferably, at most, 5 mm apart with 0-mm skip) will also be considered to have experienced progression. The transition from a non measurable lesion to a measurable lesion resulting in progression can theoretically occur with relatively small increases in tumor size (e.g., a 9×9 mm lesion [non measurable] increasing to a 10×11 mm lesion [measurable]). Ideally, the change should be significant (> 5 mm increase in maximal diameter or $\geq 25\%$ increase in sum of the products of perpendicular diameters of enhancing lesions). In general, if there is doubt about whether the lesion has progressed, continued treatment and close follow-up evaluation will help clarify whether there is true progression.

Note that if there is uncertainty regarding whether there is progression, the patient may continue on treatment and remain under close observation (e.g., evaluated at 4-week intervals). If subsequent evaluations suggest that the patient is in fact experiencing progression, then the date of progression should be the time point at which this issue was first raised.

Stable disease (SD)

All of the following criteria must be met:

- a. Does not qualify for CR, PR, or progression.
- b. All measurable and non-measurable sites must be assessed using the same techniques as baseline.

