2.5.1 Primary endpoint

PFS rate at 6 months (PFS6) as defined by RANO criteria assessed by the investigator will be the primary endpoint.

[figure not shown]
Non Surgery Group: PFS is defined as the number of days from the first day of treatment to the date of the first documented disease progression or date of death, whichever occurs first.

Surgery Group: PFS is defined as the number of days from the first day of treatment after surgery to the date of the first documented disease progression or date of death, whichever occurs first.

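### SAP 2.2 builds the success-deciding per-protocol set on no deviations of any kind, against Protocol 10.1.3 and SAP Table 2-3, and the SAP drops two protocol-planned PFS analyses without declaring it

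*SAP*

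**What the plan says.** **Deviations.** Protocol 10.1.3 admits patients to the PPS with a scan beyond 8 weeks "unless disease progression is observed before that time, and no major protocol deviations". It adds: "All major protocol deviations leading to exclusion from the PPS will be detailed in the Reporting and Analysis Plan". SAP 2.2 keeps the scan condition but drops the word *major*: "a follow-up tumor assessment >8 weeks after starting treatment unless disease progression is observed before that time, and no protocol deviations". Table 2-3 in the same section then lists six IDs that exclude from the PPS: INC01, INC02, INC04, WITH04, WITH05 and TRT05. The sentence introducing the table is permissive. Patients may be excluded "based on the protocol deviations entered in the database and/or on specific subject classification rules" in that table.

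**Sets for PFS.** Protocol 10.4.1 puts the primary analysis on the PPS (24 patients), with the FAS (34) in support. Protocol 10.4.4 applies the Bayesian model to the FAS, and Kaplan-Meier to the PPS and FAS separately. SAP 2.5.2 updates the model with PPS patients only. SAP 2.5.4 gives Kaplan-Meier for all patients pooled and names no set, so the general rule applies: "Unless otherwise specified the FAS will be the default analysis set used for all analyses". For ORR and OS (SAP 2.7.1, 2.7.2) both sets are kept.

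**Early death.** The scan rule, identical in both documents, exempts only observed progression. SAP 2.5.1 runs PFS "to the date of the first documented disease progression or date of death, whichever occurs first". Protocol Appendix 3 (14.3.2, progressive disease item e) counts as progression: "Failure to return for evaluation due to death or deteriorating condition".

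**Declared changes.** SAP section 4 lists one, the interim analysis that was not performed.

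**The concern.** The PPS alone feeds the success rule, so its definition should allow only one build. Here a programmer following the SAP sentence removes every patient with any recorded deviation, while one following Table 2-3 removes only those with a listed ID. The study is open-label, and Protocol 8.6 has the study team monitor the primary endpoint as data accrue. The choice should therefore be settled in the text and not left to judgement at analysis.

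The dropped analyses matter for a related reason. Under the SAP, the PPS result is a Bayesian Weibull posterior and the only other PFS result is a Kaplan-Meier estimate on (by default) the FAS. The two differ in method and in population, so a gap between them cannot be attributed to either. The protocol's plan allowed each comparison with one of the two held fixed.

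The early-death wording raises a smaller question: whether a patient who dies before the first post-baseline scan could fall out of the primary set although the death is a PFS event.

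**Working it through.** **1. Text comparison**

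| Item | Protocol | SAP | Declared in SAP 4? |
|---|---|---|---|
| Excluding deviations | major, listed in the analysis plan (10.1.3) | any (2.2 sentence) or six IDs (Table 2-3) | no |
| Bayesian PFS6 | PPS, and FAS in support (10.4.2, 10.4.4) | PPS (2.5.2) | no |
| Kaplan-Meier PFS | PPS and FAS separately (10.4.4) | no set named, FAS by default (2.5.4) | no |
| ORR, OS | PPS and FAS (10.5.2) | PPS and FAS (2.7.1, 2.7.2) | unchanged |
| Scan-rule exemption | observed progression (10.1.3) | observed progression (2.2) | unchanged |

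SAP 2.3.1 tabulates all deviations and, separately, those leading to exclusion from analysis sets. That split and Table 2-3 would have little purpose if every deviation excluded from the PPS.

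**2. Reproducing the plan's figures.** Inputs from Protocol 10.4.2 and 10.8: Weibull PFS, log scale parameter Normal(0, SD 2.236), shape Exponential(1), time in months, one patient per month, interim at 10 and final at 24. Success requires P(PFS6≥40%) > 0.50 and P(PFS6≥25%) > 0.80. A grid posterior gives prior probabilities of 0.648 for PFS6 below 16% and 0.258 for PFS6 above 40%, against the stated 65% and 25%. Success at true PFS6 50% is 88.5% with exponential PFS and no dropout, and 86.6% with 17.0 events under an assumed 2% monthly dropout. The protocol states 86.1% and about 17 events.

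**3. Size of the deviation wording.** The documents give no deviation rate, so the PPS size is varied as an assumption, with exclusions unrelated to outcome, no interim (SAP section 4) and 2,000 simulated trials per cell:

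| PPS size | P(success), true 50% | P(success), true 25% |
|---|---|---|
| 24 | 89.4% | 2.6% |
| 20 | 87.4% | 3.8% |
| 18 | 85.2% | 5.8% |
| 16 | 83.8% | 6.4% |
| 12 | 81.6% | 11.2% |

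A smaller set separates good from poor activity less well in both directions. The estimate itself is not pushed one way: in random subsets of 22, 19 and 17 from 24 at true PFS6 40%, the mean posterior stays at 0.397 to 0.400, while the 95% interval widens from 0.31 to 0.32, 0.34 and 0.36.

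**4. Size of the early-death wording, if item (e) were ignored.** Take x of 24 patients event-free and censored at 6 months, with the 24 − x failures at the quantiles of an exponential whose 6-month survival is x/24. Add k removed deaths back at month 0.5, 1.0 or 1.5 (ranges show the three times). The values are P(PFS6≥40%):

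- 9/24: 0.41. Fails with or without added deaths.
- 10/24: 0.576, a success. One death added (10/25 = 40.0%): 0.496 to 0.503, on the threshold. Two added (10/26 = 38.5%): 0.418 to 0.430, a failure.
- 11/24: 0.728. With one, two or three added: 0.655 to 0.662, 0.579 to 0.590, 0.501 to 0.517. Success throughout.
- 12/24: still 0.654 or more with three added. Success throughout.

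Within 9 to 12 of 24, the verdict can change only at 10/24.

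**The case against.** The best defence on deviations is that dropping *major* is a one-word slip that the rest of the SAP resolves. The protocol delegates the list, Table 2-3 is evidently that list, and SAP 2.3.1 treats excluding deviations as a subset. This is probably the intended reading, and it limits the harm. It does not settle the text, because the linking sentence lets database deviations exclude as well as, or instead of, the table.

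On the analysis sets, ORR and OS remain on both, and a Kaplan-Meier estimate on the FAS by default still sits beside the PPS posterior. That is some cross-check, but not the one the protocol planned. A reader might also ask for a run in all treated fusion/mutation patients, because the FAS includes amplification patients enrolled before Amendment 2 (Protocol 10.1.2). The protocol never planned such a run, so its absence is not a departure.

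A tempting stronger reading is that the scan rule removes early deaths and inflates PFS6. The documents do not support this. The wording comes from Protocol 10.1.3, so it is not an SAP change. Item (e) carries no restriction on cause of death, and a patient who dies before the Cycle 3 Day 1 scan has on its face failed to return because of death. Elsewhere Appendix 3 names both events ("Participants who exhibit objective disease progression or die prior to the end of Cycle 1 will also be considered evaluable"), but that passage concerns evaluability for response, not PPS membership. The documents give no share of early deaths that item (e) would miss. What stands is that the PPS rule does not point to item (e).

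**Conclusion.** Two departures from the protocol hold on the text and should be fixed. The SAP's PPS sentence contradicts both Protocol 10.1.3 and Table 2-3, and the Bayesian FAS run and the PPS Kaplan-Meier analysis have gone without a declaration in section 4.

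The likely cost of the deviation wording is a smaller PPS and less precision. The figures above are conditional on assumed set sizes and on deviations unrelated to outcome. A reader might infer bias in PFS6 from this wording, but nothing in the documents shows that unlisted deviations are related to outcome.

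The early-death point is minor. With item (e) applied there is no bias. Without it, one or two removed deaths could matter at 10 of 24 event-free and at no other count from 9 to 12, given up to three such deaths and the event times assumed.

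**What to change.** All changes are in the SAP.

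1. In 2.2, require no major protocol deviations, as listed in Table 2-3, and make the sentence above the table say that the table decides PPS exclusion for deviations.
2. Restore the Bayesian model on the FAS and name the PPS and FAS in the 2.5.4 Kaplan-Meier analysis, or declare and justify their removal in section 4.
3. In the scan rule, cross-reference Protocol Appendix 3, progressive disease item (e), so that a patient who dies before the first post-baseline scan stays in the PPS as a PFS event. This clarifies the protocol rule and does not change it, so no amendment under Protocol 12.1 is called for.

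Optional: a sensitivity run of the 2.5.2 model in all treated fusion/mutation patients, keeping the exclusion in Protocol 10.4.1 of group 2 surgical patients with no post-surgical dose. It would show directly what the PPS exclusions did to PFS6.

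The cost is a few sentences and two reruns of existing programs, or three with the optional run. No new data are needed.

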4.1 Description of study design

This is a multi-center, open label, phase II study, with 2 groups of patients. BGJ398 will be administered once daily as an oral single agent in 28-day cycles, on a “3 weeks on, one week off schedule.” The study will enroll patients with recurrent GBM and/or other glioma subtypes, whose tumors harbor FGFR1-TACC1, FGFR3-TACC3 fusion and/or activating mutation in FGFR1, FGFR2 or FGFR3 gene.

Group 1 will target patients with RANO tumor progression not eligible for surgical resection. As the primary endpoint is the 6 month progression-free survival rate. Additionally, patients who recently underwent resection and are post-operative without RANO tumor progression may also be eligible for group 1 assuming all inclusion/exclusion criteria are met and most recent surgery has occurred within six weeks of planned first treatment dose.

[figure not shown]
Group 2 will target patients who will have cytoreductive surgery for recurrent disease as part of their routine care. Patients enrolled to group 2 will receive BGJ398 for 5 to 10 days prior to resection.

Following recovery from surgery (a minimum of 2 weeks and no more than six weeks post operatively unless agreed otherwise between Novartis and the Investigator, on a case by case basis), these patients will receive BGJ398 in 28-day cycles, as for patients in group 1. If a patient assigned to group 2 does not undergo planned surgical resection, then the patient will be allowed to continue therapy as per group 1. If a patient enrolled to group 2 needs to undergo surgical resection sooner than initially planned (and having had less than 5 days of BGJ398), then the patient will still be allowed to continue therapy post-surgically as per group 2 regardless of the number of days the patient received BGJ398 pre-surgically.

A total of 34 patients will be enrolled, and it is expected that the ratio of patients in group 1 and group 2 will be approximately 2:1, based on previous GBM trials (Stupp et al 2006, Wong et al 1999; Lamborn et al 2008; Wong et al 2011; Hofer et al 2011; Wen et al 2009; Norden et al 2008; Yung et al 2000). Please see Section 10: Statistical Methods and Data for details.

In order to assess the antitumor activity of BGJ398, patients will be evaluated for tumor response and progression by Gd-enhanced MRI every 8 weeks until disease progression or discontinuation from study using RANO criteria.

Figure 4-1 Study design

Molecular pre-screening

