7.1.3 Treatment period

During the treatment period, the patient is obliged to follow the investigators instructions with regards to contraception, concomitant medications and dosing regimen. There is no fixed duration; patients may continue treatment with the study drug until the development of an unacceptable toxicity that precludes any further treatment, disease progression, and /or treatment is discontinued at the discretion of the Investigator or by patient refusal.

For the patients included in group 2 (surgical group), there is a fixed treatment duration of 5 to 10 days before surgery. The last dose should be on the day of surgery, or the day before at the discretion of the investigator. At a minimum of 2 weeks post-surgery, patients may resume study treatment with BGJ398 until experiencing unacceptable toxicity, disease progression and/or the treatment is discontinued at the discretion of the investigator or by patient refusal (withdrawal of consent). Day 1 of treatment following surgery will be considered to be Cycle 1 Day 1. For details of assessments during the treatment period, refer to [Table 7-1](#).

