7.2 Assessment types

7.2.1 Efficacy assessments

Tumor response and progression will be assessed by the Investigator, using the Response Assessment in Neuro-Oncology (RANO) Working Group ([Wen et al. 2010](#)) as detailed in [Appendix 3](#).

Each patient will be evaluated for all potential sites of tumor lesions at Screening and every 8 weeks after starting study treatment until disease progression.

On-study tumor assessments have a ± 7 day window, except for the first post-baseline tumor assessment and for confirmatory scans (4 weeks +7 day window only). The first post-baseline tumor assessment should be performed on day 1 of cycle 3 (+7 day window permitted) after starting treatment. There will be a tumor assessment at the End of Treatment (+ 7 days) if the patient discontinues for any reason other than disease progression and the last tumor assessment has been performed > 28 days prior to this day.

For group 1, the baseline scan must occur within 28 days of treatment initiation. For group 2, patients undergoing surgery, per standard of care, a MRI should be performed within 72 hours after surgery ([Wen et al. 2010](#)). This scan can function as the baseline scan if BGJ398 therapy is initiated within four weeks of surgery. If BGJ398 is initiated after 4 weeks following surgery, a baseline scan must be performed within 7 days of starting BGJ398. Subsequent post baseline scans will be performed as described above. For group 2 patients who do not undergo surgery the baseline scan will be defined as per group 1.

Note: in case a patient cannot tolerate MRI, the patient may still participate in the study following discussion between Novartis and the investigator. In this case, all efficacy assessments will be made by CT scans for that patient. Efficacy assessments should be performed by using the same technique throughout the study for each patient.

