7.2.2.6 Radiological examinations

7.2.2.6.1 MRI scan (or CT if patient is unable to undergo MRI).

Please refer to details in [Section 7.2.1](#) and [Appendix 3](#). The same modality (MRI/CT) must be used throughout the study

First post baseline scan occurs cycle 3 day 1; subsequent scans occur every 8 weeks until unacceptable toxicity or disease progression, whichever occurs first.

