2.1.1 General definitions

Investigational drug and study treatment

Investigational drug refers to the BGJ398 only.

Study treatment = investigational drug.

Date of first administration of investigational drug

The date of first administration of investigational drug is defined as the first date when a non-zero dose of investigational drug BGJ398 is administered and recorded on the Dosage Administration Record (DAR) (e)CRF. The date of first administration of investigational drug will also be referred as the start date of investigational drug.

Date of last administration of investigational drug

The date of last administration of investigational drug is defined as is the last date when a nonzero dose of investigational drug is administered and recorded on DAR (e)CRF. The date of last administration of investigational drug will also be referred as the last date of investigational drug.

Study day

The study day, describes the day of the event or assessment date, relative to the reference start date.

The study day is defined as:

- The date of the event (visit date, onset date of an event, assessment date etc.) – reference start date + 1 if event is on or after the reference start date;
- The date of the event (visit date, onset date of an event, assessment date etc.) – reference start date if event precedes the reference start date.

The reference date for all assessments (safety, efficacy, ████ etc) is the start date of study treatment.

The study day will be displayed in the data listings. If an event starts before the reference start date, the study day displayed on the listing will be negative.

Time unit

A year length is defined as 365.25 days. A month length is 30.4375 days (365.25/12). If duration is reported in months, duration in days will be divided by 30.4375. If duration is reported in years, duration in days will be divided by 365.25. A week length is 7 days. If duration is reported in weeks, duration in days will be divided by 7.

Baseline

For **non-efficacy assessments**, **Baseline** is the last available and valid assessment performed or value measured within 21 days before the first administration of study treatment, unless otherwise stated under the related assessment section. Baseline can be the day before first treatment administration or the same day as first treatment administration if a pre-dose assessment/value is available (e.g., ECG, [REDACTED]).

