In order to summarize ECOG performance status, ████ vital signs, and other data collected over time (including unscheduled visits), the assessments will be time slotted. The following general rule will be applied in creating the assessment windows: If more than one assessment is done within the same time window, the assessment performed closest to the target date will be used. If 2 assessments within a time window are equidistant from the target date, then the earlier of the 2 assessments will be used. If multiple assessments on the same date then the worst case will be used. Data from all assessments (scheduled and unscheduled), including multiple assessments, will be listed.

Table 2-1 Time windows for assessments

Assessment	Target day of assessment	Time Interval
Baseline		≤ Day 1
Cycle 1 Day 15	15	Day 2 to day 21
Cycle 2 Day 1	29	Day 22 to day 42
Cycle 3 Day 1	57	Day 43 to day 63
Cycle 3 Day 15	71	Day 64 to day 77
Cycle 4 Day 1	85	Day 78 to day 98
Cycle k Day 1 (k≥5)	$d=(k-1)*28+1$	Day d-14 to day d+13
End of Treatment		Assessment taken at the end of treatment visit

Last contact date

The last contact date will be derived for patients not known to have died at the analysis cut-off using the last complete date among the following:

Table 2-2 Last contact date data sources

Source data	Conditions
Last contact date/last date patient was known to be alive from Survival Follow-up page	- Patient status is reported to be alive, lost to follow-up or unknown.
Start/End dates from further antineoplastic therapy	Non-missing medication/procedure term.

Source data	Conditions
Start/End dates from drug administration record	Non-missing dose. Doses of 0 are allowed.
End of treatment date from end of treatment page	No condition.
RANO assessment date	Evaluation is marked as 'done'.
Laboratory ████ collection dates	Sample collection marked as 'done'.
Vital signs date	At least one non-missing parameter value
Performance Status date	Non-missing performance status
Start/End dates of AE	Non-missing verbatim term

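### The per-protocol rule asks for a scan more than 8 weeks after starting treatment, but the first scan falls due at exactly 8.0 weeks, so one sentence can yield two primary sets, and the stricter one loses mainly early failures

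*SAP*

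**What the plan says.** SAP 2.2 and Protocol 10.1.3 define the PPS with the same scan condition: "a follow-up tumor assessment >8 weeks after starting treatment unless disease progression is observed before that time". Protocol 10.4.1 makes the PPS, planned at 24 patients, the primary analysis set. The success rule in Protocol 10.4.2 and SAP 2.5.2 is applied to it.

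The scan calendar comes from other sections:

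- Protocol 7.2.1, repeated in SAP 2.7: "The first post-baseline tumor assessment should be performed on day 1 of cycle 3 (+7 day window permitted) after starting treatment".
- Protocol 4.1: "BGJ398 will be administered once daily as an oral single agent in 28-day cycles".
- SAP Table 2-1 gives Cycle 3 Day 1 a target of study day 57, within the slot "Day 43 to day 63".
- SAP 2.1.1 counts study day as event date minus "reference start date + 1 if event is on or after the reference start date", and states that "A week length is 7 days".
- Protocol 7.2.2.6: "First post baseline scan occurs cycle 3 day 1; subsequent scans occur every 8 weeks until unacceptable toxicity or disease progression".
- Protocol 7.1.3, for the surgical group: "Day 1 of treatment following surgery will be considered to be Cycle 1 Day 1".

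Neither document says how a scan, or a progression, at exactly 8 weeks is classified, or which first dose starts the 8-week clock in operated Group 2 patients.

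**The concern.** The scan condition is a strict inequality, and its threshold coincides with the due date of the first scan. Because scanning ends at progression, a patient who progresses on that scan has no later scan on which to qualify. A patient who stays progression-free qualifies at the next 8-weekly scan. An exclusion at this boundary therefore falls mainly on early failures, and removing them raises the estimated PFS6.

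At stake is the set that decides study success. Two programmers could build different sets from the same sentence. The trial is open-label, so an undefined boundary might be settled by people who can see the outcomes it affects.

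**Working it through.** **1. Timing.** With 28-day cycles, Cycle 3 Day 1 is study day (3 − 1) × 28 + 1 = 57, which matches SAP Table 2-1. The first dose is day 1, so elapsed time is 57 − 1 = 56 days, and 56 / 7 = 8.0 weeks. That is not more than 8.

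**2. Window.** The permitted days are study days 57 to 64, or 56 to 63 elapsed days. Day 57 fails the strict inequality; days 58 to 64 pass. One of eight permitted days is affected.

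**3. Outcomes for a Group 1 patient scanned on day 57, strict reading** (elapsed days; the time in question is 8 weeks):

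| Day 57 scan | Afterwards | In the PPS? |
|---|---|---|
| Progression | No further scans | No: scan not after 8 weeks, progression not before 8 weeks |
| Stable | No later scan or documented progression | No |
| Stable | Later scan | Yes, through the later scan |

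**4. Operated Group 2.** Counted from the first pre-surgical dose, Cycle 3 Day 1 falls between 5 + 14 + 56 = 75 and 10 + 42 + 56 = 108 days later on the standard schedule, and passes. Counted from post-surgical Cycle 1 Day 1, it falls at 56 days, as in Group 1.

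**5. The plan's own operating characteristics.** A simulation with the stated priors, one patient per month, the interim at 10 and the final analysis at 24, exponential PFS (assumed) and nobody dropped gives a success probability of 0.853 at true PFS6 of 50%, against 0.861 in Protocol Table 10-2. At 25% it gives 0.013, against 0.026. The table is thus reproduced to within about two points when no patient is lost at this boundary.

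**6. Illustrative size.** Assumptions: exponential PFS; true PFS6 of 25%; every event by week 8 found at the first scan; the 2:1 group ratio of Protocol 4.1 applied to 24 patients, so 16 in Group 1; only Group 1 exposed; a share q of first scans on exactly day 57.

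- Share with an event by day 56: 1 − 0.25^(56/182.6) = 0.346.
- Patients lost: 16 × 0.346 × q.
- Apparent PFS6: (24 × 0.25) / (24 − patients lost) = 6 / (24 − patients lost).

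| q | Patients lost | Apparent PFS6 |
|---|---|---|
| 1/8 | 0.7 | 25.7% |
| 1/4 | 1.4 | 26.5% |
| 1/2 | 2.8 | 28.3% |
| 1 | 5.5 | 32.5% |

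**The case against.** The strongest reply is that the clause has a second natural reading. The time it names can be the required assessment itself, at some point after 8 weeks. Day 57 precedes any such point, so progression on day 57 satisfies the exception and the patient stays in. The week count is also open. The SAP's study-day convention and its exposure formula both add one day, and 57 / 7 = 8.14 would pass. Both points stand. They establish that the text is ambiguous, not that the ambiguity is harmless.

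Several stronger readings are tempting and should not be drawn:

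- *All on-schedule first scans fail.* The grace period is part of the schedule, and seven of its eight days pass. Stable patients with a later scan also enter. Protocol 7.2.1 adds an end-of-treatment scan when a patient stops for a reason other than progression and the last scan was more than 28 days earlier, and Protocol 7.1.5 continues 8-weekly scans after that.
- *Operated Group 2 patients always pass.* SAP 2.1.1 dates first administration from the first non-zero dose, which is pre-surgical. But the baseline-scan rule in Protocol 7.2.1 uses the start of BGJ398 to mean the post-surgical start, and Protocol 10.4.1 starts PFS there. The documents leave the clock unresolved.
- *Two to four of 24 patients are lost.* With q at one quarter or one half, this needs all 24 exposed (24 × 0.346 × q = 2.1 or 4.2; apparent PFS6 27.4% or 30.2%). It cannot be combined with Group 2 passing, and nothing in the documents supports a particular q.

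The 0.346 also counts every event by day 56. Deaths and clinical progressions recognised earlier are included, and progression documented before 8 weeks already meets the exception, so the illustration overstates that component. RANO as given in Appendix 3 also counts failure to return because of death or deterioration as progression, which retains some early deaths.

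Protocol 10.4.4 repeats the analysis on the Full Analysis Set, where these patients remain visible. That is not a clean check, because the set also contains the amplification patients enrolled before Amendment 2 (Protocol 10.1.2), and Protocol 10.4.1 puts the efficacy focus on the PPS.

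**Conclusion.** The concern holds as a boundary defect in the definition of the primary set. The scan rule and the scan calendar meet at exactly 8.0 weeks. One reasonable coding then excludes Group 1 patients who progress on day 57, and those stable on day 57 with no later scan or documented progression; another keeps them. The stricter coding acts in one direction and raises PFS6.

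The size is not determined by the documents, because it turns on how many first scans fall on exactly day 57. Under the stated assumptions, with one quarter or one half of first scans on that day, about 1.4 or 2.8 of 24 patients are lost and a true PFS6 of 25% appears as about 27% or 28%. A reader might infer that the primary result is certain to be biased, or badly so. The documents do not support that: both the reading and the share of day-57 scans are open. What they do support is that membership of the success-deciding set should not depend on whether a scan was booked for day 57 or day 58.

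**What to change.** In Protocol 10.1.3 and SAP 2.2, replace the scan clause with:

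> a post-baseline tumor assessment on or after Cycle 3 Day 1 (at least 56 days after Cycle 1 Day 1; for operated Group 2 patients, counted from post-surgical Cycle 1 Day 1), or disease progression or death at any time up to and including that assessment.

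This admits all eight permitted days, keeps early progressions and deaths, and gives both groups the same clock.

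The cost is one sentence in each document and one programming condition. No visit, prior, success threshold or sample size changes. The downside for the sponsor is that PFS6 may come out slightly less favorable, because early failures stay in.
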